4. ABSTRACT

- **Protocol title**

Treatment patterns and clinical outcomes among venous thromboembolism patients treated with anticoagulants after the entry of non-vitamin K antagonist oral anticoagulants in Korea

- **Protocol version and date**

2.0, 27 Apr 2022

- **Rationale and background**

Venous Thromboembolism (VTE), which includes deep vein thrombosis (DVT) and pulmonary embolism (PE), is a major cause of morbidity, mortality and healthcare expenditure. Although the occurrence of VTE in the Asian population has been lower than that in Western populations, its incidence has been reported to have increased rapidly in recent years.

For pharmacologic treatment of patients with VTE without cancer, the American College of Chest Physicians (CHEST) guidelines recommend the use of Non-Vitamin K antagonist oral anticoagulants (NOACs) over Vitamin K Antagonists (VKAs), with supporting evidences suggesting that each NOAC (e.g., apixaban) is effective at preventing recurrent VTE. In more recent treatment guidelines for the management of VTE released by the American Society of Hematology (ASH), NOACs are still recommended over VKAs for the initial management of VTE. NOACs are classified as a new generation of anticoagulants with approved indications of the risk reduction of stroke and embolism in nonvalvular atrial fibrillation (NVAF) as well as prophylaxis and treatment of DVT and PE.

All NOACs became available as the first-line treatment of acute VTE in Korea after reimbursement expansion in May 2015. However, despite the increasing use of NOACs among VTE patients, there are still limited real-world evidence that assess treatment patterns as well as effectiveness and safety of the different anticoagulants especially among Asian population.

- **Research question and objectives**

Research question

- What is the real-world evidence of anticoagulant treatment for patients with VTE that can be found in the nationwide claims database in Korea?

The current study will take place in two phases:

Phase I involves a descriptive assessment of VTE patient characteristics and treatment patterns in Korea as well as detailed power calculations for comparative analyses.

Phase II involves analyses of comparative safety between each NOAC and warfarin. These analyses will be implemented if there is sufficient power to enable scientifically valid inferences.

Primary objectives of Phase I of the study

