- Had a record of active cancer, defined as first diagnosis of cancer with V code (a special code applied to patients with confirmed diagnosis of cancer by Korean Ministry of Health and Welfare for reimbursement for 5 years or longer if recurrent/metastatic) within the past 6 months of period prior to index date; or receiving anti-cancer treatment (chemotherapy, radiation therapy, or cancer-related surgery) under cancer diagnosis with V code within the past 6 months period prior to index date

Follow-up

- **Phase I of the study:** Patients will be followed-up from the index date until the earliest of in-hospital death or end of the study period (31 Dec 2019).
- **Phase II of the study:** Patients will be followed-up from the index date until the earliest of outcome occurrence (bleeding event), treatment discontinuation, switch to another anticoagulant, in-hospital death, or end of the study period (31 Dec 2019), where patients will be considered to have discontinued treatment when new prescription is absent within the 30-day grace period after the end of the former prescription.

- **Variables**

Exposure(s)

- Anticoagulant therapy (PAC [LMWH, UFH, others], NOACs [apixaban, dabigatran, rivaroxaban, edoxaban], warfarin).

Outcome(s)

- **Phase I of the study:** sociodemographic and clinical characteristics of patients with VTE, utilization of index anticoagulant treatment, treatment patterns (including treatment interruption, switching, complete discontinuation), overall treatment duration, and clinical events preceding first treatment change
- **Phase II of the study:** Primary or secondary diagnosis with major bleeding (by site: intracranial, gastrointestinal [GI], and other sites) after the index date

Covariate(s)

- Sociodemographics (age, sex) will be assessed on the index date. Clinical characteristics including comorbidities, previous use of medications, and the number of outpatient visits will be assessed within the 6-month period prior to the index date

- **Data sources**

- South Korea's Health Insurance and Review Assessment Service (HIRA) database

- **Study size**

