Baseline sociodemographic characteristics (e.g., age, sex) will be assessed on the index date, whereas clinical characteristics (comorbidities, previous use of medications, Charlson comorbidity index [CCI], HAS-BLED scores, initial presentation of VTE, number of outpatient visits) will be assessed in the 6-month period prior to the index date except when otherwise specified in section 9.3 *Variables* (Figure 2).

[figure not shown]

Figure 2. Overall study schematic

- Baseline conditions included: Charlson comorbidity index, HAS-BLED scores, comorbidities (antiphospholipid syndrome, asthma, cancer, chronic obstructive pulmonary disease, chronic kidney disease, chronic liver disease, diabetes mellitus, fracture, heart failure, hyperlipidemia, hypertension, ischemic heart disease, myocardial infarction, stroke, trauma), previous use of medications (corticosteroids, nonsteroidal anti-inflammatory drugs, angiotensin-converting enzyme inhibitors,

- angiotensin II receptor blockers, antiplatelet agents, azole antifungal agents, β -blockers, calcium-channel blockers, selective serotonin reuptake inhibitors, proton pump inhibitors, diuretics, thiazides, vasodilators, estrogens, cyclooxygenase-2 inhibitors), initial presentation of VTE (DVT, PE, both DVT and PE), number of outpatient visits
- b. Earliest of: outcome of interest (major bleeding event), treatment discontinuation, switch to another anticoagulant, in-hospital death, end of the study period (31 Dec 2019)

Note: Dx, diagnosis; NOAC, non-vitamin K antagonist oral anticoagulant; Rx, prescription; VTE, venous thromboembolism; PE, pulmonary embolism

Within this study cohort, we will describe the treatment patterns of anticoagulants prescribed for VTE treatment throughout the period of follow-up, defined as the period from the index date to the end of the study period. Moreover, if feasible, we will also examine the risk of major bleeding overall and by site, associated with each NOAC use, as compared with warfarin.

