9.3. Variables

Exposure

- **Phase I of the study:** PAC (UFH [Anatomical Therapeutic Chemical [ATC] code: B01AB01], LMWH [B01AB04, B01AB05, B01AB06, B01AB12]), VKA (warfarin [B01AA03]), NOACs (apixaban [B01AF02], rivaroxaban [B01AF01], edoxaban [B01AF03], dabigatran [B01AE07])
- **Phase II of the study:** Apixaban (B01AF02), Rivaroxaban (B01AF01), Edoxaban (B01AF03), Dabigatran (B01AE07), Warfarin (B01AA03)

Outcome(s)

- **Phase I of the study**

- Sociodemographic and clinical characteristics of patients with VTE who initiated anticoagulants.
- Utilization of different anticoagulants at treatment initiation. Patients will be classified based on their index anticoagulant treatment received within 30 days after being diagnosed with VTE.
- Treatment interruption from the index anticoagulant treatment, which will be defined as when a patient has a gap with no new treatment within 30 days of the estimated end of supply, but subsequently restarts the index treatment after this period.[21] The time to treatment interruption will be defined as the period from the index date to the date of treatment interruption.
- Treatment switching will be defined as a prescription of another anticoagulant therapy that is started after the treatment initiation of the index anticoagulant treatment and within 30 days after the estimated end of supply of the index anticoagulant drug (exposure to the new anticoagulant treatment must last for at least 30 days to be considered as a treatment switch). The time to treatment switch will be defined as the period from the index date to the date of treatment switch.

Exemption: As heparin can be initiated at acute stage of DVT/PE before clinical decision to use OAC, a switch from initial heparin treatment to an OAC within 2 weeks after heparin treatment initiation will not be considered a treatment switch.

- Treatment discontinuation (complete discontinuation; no reinitiation) will be defined as when a patient who ended their first continuous treatment episode with the index anticoagulant treatment without switching, and subsequently have no further prescriptions for that respective anticoagulant treatment during all available follow-up time. The time to treatment discontinuation will be defined as the period from the index date to the date of treatment discontinuation.

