- Overall anticoagulant treatment duration will be defined as the time period from the index date to the earliest of treatment interruption, switch, or discontinuation.
- If a patient has evidence of a repeat prescription within 30 days of the end of their prescription and does not experience any of the above events (treatment interruption, switch, or discontinuation), they will be assumed to be persistent on treatment.[21]
- Clinical event preceding first treatment change will be defined as occurrence of any event listed below within 30 days before treatment interruption, switch, or discontinuation. A new clinical event will be considered 'new' when it occurs for the first time within a 6-month period for acute conditions (arterial

thromboembolism, ischemic stroke, transient ischemic attack, myocardial infarction, angina pectoris, acute kidney injury, and abnormal liver function) and 5-years for chronic conditions (cancer, chronic kidney disease, and liver disease). A patient may contribute to multiple events.

- ① Major bleeding (as defined in Table 2)
- ② Complications of VTE: post-thrombotic syndrome and chronic thromboembolic pulmonary hypertension
- ③ Thromboembolism: PE diagnosis in patients with index event as DVT only, new diagnosis of arterial thromboembolism, ischemic stroke, transient ischemic attack, myocardial infarction, or angina pectoris
- ④ Major surgery: orthopedic surgeries (knee arthroplasty, hip arthroplasty, and hip fracture surgery), cancer surgeries (stomach, colorectal, hepatobiliary, pancreatic, breast, ovarian, cervical, renal, bladder, prostate, lung, and esophageal cancers, and brain tumors), and benign surgeries (myomectomy, oophorectomy, and transurethral resection of the prostate)
- ⑤ Cancer-related event (among non-active cancer patients only): new diagnosis of active cancer
- ⑥ Kidney function change: new diagnosis of chronic kidney disease or acute kidney injury
- ⑦ Liver function change: new diagnosis of liver disease or abnormal liver function

- **Phase II of the study**

- Major bleeding will be defined using primary or secondary diagnosis codes according to the ICD-10 diagnostic codes shown in Table 2 and classified by site (intracranial, gastrointestinal [GI], and other sites) [22].

Table 2. Definition of major bleeding by site

Major bleeding	ICD-10 diagnosis code	Diagnostic definition

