8.2. Study population

The study cohort will be defined as patients diagnosed with VTE between 1 Mar 2013 and 30 Jun 2019. The cohort entry will be defined as the date of incident VTE diagnosis. The index date will be defined as the date of first prescription for anticoagulants within 30 days after the index VTE event. The length of the exclusion assessment window will vary depending on the condition, from 12-months at minimum to anytime prior to index date. The following patients will be excluded: A record of VTE diagnosis within the 12-month period prior to the index VTE encounter, diagnosed with atrial fibrillation, atrial flutter, mechanical heart valve replacement or mitral stenosis anytime prior to index date, had a record of Inferior Vena Cava filter anytime prior to index date, received anticoagulatory therapy within the 12-month period prior to index VTE encounter to restrict to new users of anticoagulatory therapy, prescribed two different anticoagulants on the same index date to prevent exposure misclassification, had a record of pregnancy within the 9-month period prior to index date, and for the Phase II of the study only, had a record of active cancer within six months period prior to index date.

Baseline sociodemographic characteristics (e.g., age, sex) will be assessed on the index date, whereas clinical characteristics (comorbidities, previous use of medications, Charlson comorbidity index [CCI], HAS-BLED scores, initial presentation of VTE, number of outpatient visits) will be assessed in the 6-month period prior to the index date except when otherwise specified in section 8.4 *Variables* (Figure 2).

Within this study cohort, we will describe the treatment patterns of anticoagulants prescribed for VTE treatment throughout the period of follow-up, defined as the period from the index date to the end of the study period. Moreover, if feasible, we will also examine the risk of major bleeding overall and by site, associated with each NOAC use, as compared with warfarin.

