8.4. Variables

Exposure

- **Phase I of the study:** PAC (UFH [Anatomical Therapeutic Chemical [ATC] code: B01AB01], LMWH [B01AB04, B01AB05, B01AB06, B01AB12], VKA (warfarin [B01AA03]), NOACs (apixaban [B01AF02], rivaroxaban [B01AF01], edoxaban [B01AF03], dabigatran [B01AE07])
- **Phase II of the study:** Apixaban (B01AF02), Rivaroxaban (B01AF01), Edoxaban (B01AF03), Dabigatran (B01AE07), Warfarin (B01AA03)

Outcome(s)

- **Phase I of the study**

- Sociodemographic and clinical characteristics of patients with VTE who initiated anticoagulants.
- Utilization of different anticoagulants at treatment initiation. Patients will be classified based on their index anticoagulant treatment received within 30 days after being diagnosed with VTE.
- Treatment interruption from the index anticoagulant treatment, which will be defined as when a patient has a gap with no new treatment within 30 days of the estimated end of supply, but subsequently restarts the index treatment after this period.[1] The time to treatment interruption will be defined as the period from the index date to the date of treatment interruption.
- Treatment switching will be defined as a prescription of another anticoagulant therapy that is started after the treatment initiation of the index anticoagulant treatment and within 30 days after the estimated end of supply of the index anticoagulant drug (exposure to the new anticoagulant treatment must last for at least 30 days to be considered as a treatment switch). The time to treatment switch will be defined as the period from the index date to the date of treatment switch.

Exemption: As heparin can be initiated at acute stage of DVT/PE before clinical decision to use OAC, a switch from initial heparin treatment to an OAC within 2 weeks after heparin treatment initiation will not be considered a treatment switch.

- Treatment discontinuation (complete discontinuation; no reinitiation) will be defined as when a patient who ended their first continuous treatment episode with the index anticoagulant treatment without switching, and subsequently have no further prescriptions for that respective anticoagulant treatment during all available follow-up time. The time to treatment discontinuation will be defined as the period from the index date to the date of treatment discontinuation.
- Overall anticoagulant treatment duration will be defined as the time period from the index date to the earliest of treatment interruption, switch, or discontinuation.

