10. STATISTICAL ANALYSIS

All statistical analyses will be performed using SAS Enterprise Guide 7.1 (SAS Institute Inc., Cary, NC, USA), provided by HIRA through a virtual access machine.

Phase I of the study (descriptive)

Main Analysis

- Descriptive analysis will be conducted separately in two cohorts of non-cancer VTE and cancer VTE patients according to co-presence of active cancer.
- Sociodemographic and clinical characteristics will be summarized with means (standard deviations [STD]) or median (interquartile range [IQR]) for continuous variables and with count (proportions) for categorical variables for the three treatment groups of interest: PAC only (UFH, LMWH, UFH+LMWH), warfarin-based (warfarin, PAC/warfarin) group, NOAC-based (NOAC, PAC/NOAC) group. NOAC-based (NOAC, only group, PAC/NOAC) group. Analysis of variance, and chi-square test will be conducted for continuous variables, and categorical variables, respectively.
 - In order to distinguish between PAC bridging therapy and PAC treatment, we will apply a time restriction of 2 weeks to PAC bridging therapy.
- Temporal trend in anticoagulation therapy for VTE will be presented between 1 Mar 2013 and 30 Jun 2019. Proportions of the index OACs will be estimated according to calendar year and quarter.
- The number and percentage of patients who discontinue treatment completely, experience treatment interruption and treatment switch during their follow-up will be described by the index anticoagulant treatment received. Results will be limited to the first of each of these events for each patient. For patients experiencing a treatment switch, the new treatment will be described at the time of their first switcher per individual drug.
- The duration of the index treatment by the index anticoagulant treatment received will also be summarized in terms of days using descriptive statistics (mean [STD], median [IQR]).
- The Kaplan-Meier method will be applied to derive the empirical distribution of time to each of the treatment endpoints of interest (e.g., treatment discontinuation or switch); these analyses will be performed per index anticoagulant treatment received and no comparisons will be made. Log-rank test will be conducted at the 3-, and 6 months after treatment initiation to assess statistical significance between the survival curves. Persistent rate will also be calculated at the same time point.

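### Phase I rules allow a death outside hospital, and possibly one in hospital, to be counted as complete discontinuation with follow-up to 31 Dec 2019

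*Protocol*

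**What the plan says.** Three places define the end of Phase I follow-up, and they differ.

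- Protocol 4 (Abstract, Follow-up): "Patients will be followed-up from the index date until the earliest of in-hospital death or end of the study period (31 Dec 2019".
- Protocol 9.1 describes treatment patterns "throughout the period of follow-up, defined as the period from the index date to the end of the study period". No death is named.
- SAP 8.2 has the same rule: "defined as the period from the index date to the end of the study period". Again no death is named.

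Complete discontinuation applies to "a patient who ended their first continuous treatment episode with the index anticoagulant treatment without switching" (SAP 8.4, with matching text in Protocol 9.3). The patient must also "subsequently have no further prescriptions for that respective anticoagulant treatment during all available follow-up time" (Protocol 9.3, with matching text in SAP 8.4). Treatment duration has no death endpoint either: "Overall anticoagulant treatment duration will be defined as the time period from the index date to the earliest of treatment interruption, switch, or discontinuation".

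SAP Tables 5-8 have a Death row beside the rows for switching, continuation, discontinuation and interruption. Its source is not given, and no rule says which row a patient enters if more than one could apply. Tables 1-4 report follow-up in days. On cohorts, SAP 10 says "Descriptive analysis will be conducted separately in two cohorts of non-cancer VTE and cancer VTE patients". Protocol 9.9 does not mention deaths outside hospital and treats limitations from missing or incomplete data as not applicable.

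**The concern.** In-hospital death is the only kind of death that either document defines as an event. In claims data, a patient who dies at home while on an anticoagulant looks like one who stopped: prescriptions cease and nothing follows. Unless the rules separate the two, some reported discontinuations are deaths.

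Discontinuation and treatment duration belong to a primary Phase I objective. The same patients enter the Kaplan-Meier curves, the 3- and 6-month persistence rates and the log-rank test across the three treatment groups in Protocol 9.7. A difference between groups in unseen death would enter that test. The secondary objective is exposed too. Clinical events in the 30 days before a treatment change are read as possible reasons for it, so a bleed followed by death at home would appear as a reason for stopping. The direction of the error is known, and a larger sample does not remove it.

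**Working it through.** The plan states no Phase I figure for discontinuation, mortality or follow-up, so there is nothing to reproduce. The check traces the definitions and then shows what the size would depend on.

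**Trace: death outside hospital on treatment**

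1. The first episode ends when supply runs out, with no switch and no later prescription. Both conditions for complete discontinuation are met.
2. The death is not an in-hospital death, so even under the abstract it does not end follow-up. Follow-up runs to 31 Dec 2019.
3. Exception: if supply plus the 30-day gap runs past 31 Dec 2019, no gap is seen and the patient stays persistent.

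**Trace: death in hospital**

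1. Under the abstract, follow-up ends at death.
2. Under Protocol 9.1 and SAP 8.2 it does not, and the discontinuation conditions are met as above. Only the Death row of Tables 5-8 suggests otherwise, and it has no precedence rule.

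**Falsely credited follow-up.** This is at most the time from index to 31 Dec 2019: 2,496 days for an index date of 1 Mar 2013, and 154 days for 30 Jul 2019 (diagnosis on 30 Jun 2019 plus 30 days).

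**Size of the effect on 6-month discontinuation (illustration; all inputs assumed).** Let D be true net discontinuation at 6 months, M all-cause death on treatment by 6 months, and s the share of deaths outside hospital. Hazards are constant and independent, and in-hospital deaths are censored. With d = -ln(1-D) and m = -ln(1-M):

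observed discontinuation = 1 - exp(-(d + s·m))

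overstatement = (1-D) × [1 - (1-M)^s]

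For D = 50% and s = 25%:

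- M = 2%: 0.5 × (1 - 0.98^0.25) = 0.5 × 0.0050 = 0.3 points
- M = 5%: 0.5 × 0.0127 = 0.6 points
- M = 20%: 0.5 × 0.0543 = 2.7 points
- M = 40%: 0.5 × 0.1199 = 6.0 points

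Over D = 30-70%, M = 2-40% and s = 10-50%, the smallest value is 0.3 × (1 - 0.98^0.1) = 0.1 points and the largest is 0.7 × (1 - 0.6^0.5) = 15.8 points. If in-hospital deaths are also counted as discontinuation, s = 100% and the overstatement is (1-D) × M. With D = 50% and M = 20% that is 0.5 × 0.20 = 10.0 points.

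**Which cohort is affected more.** At equal D the overstatement rises with s·m, so the active-cancer cohort has the larger error only if its death hazard times its out-of-hospital share is larger. The death hazard in that cohort would have to exceed the non-cancer hazard by more than:

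- 0.50/0.10 = 5 times, if 50% of non-cancer and 10% of cancer deaths occur outside hospital
- 0.25/0.10 = 2.5 times, if the shares are 25% and 10%
- 1 time, if the shares are equal

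**The case against.** The strongest reply is that Phase I is descriptive with no prior hypotheses, no power figure depends on it, and the error may be a fraction of a point. That stands. It limits the severity but does not remove a bias of known direction from a primary output.

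A second reply is that the Death row shows an intention to separate deaths, and that the Figure 2 footnote lists in-hospital death. The intention is likely. But that footnote also lists major bleeding and treatment discontinuation as ends of follow-up, which fits Phase II, and nothing states precedence for Phase I.

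Third, the variable lists in Protocol 9.4 and SAP 7 include open-ended entries, so it cannot be said that the extract holds no vital status. That is fair. What can be said is that the plan describes no vital-status field or death-register link.

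A reader might infer that discontinuation is inflated most in the active-cancer cohort, because the Protocol says VTE "is a major cause of morbidity, mortality and healthcare expenditure" and that cohort is reported separately. The documents do not support this as a finding. They give neither mortality nor place of death by cohort, and a higher in-hospital share of cancer deaths could shrink or reverse the ranking. No test between the cohorts is planned, although SAP Figures 1-3 plot the curves by cancer status.

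It is also tempting to make a later claim a condition of discontinuation in the main analysis. That would condition on the future. Late entrants who truly stop would have little time to generate a claim, and true stoppers who later die could be lost. For interruption the condition adds nothing, since interruption already requires a restart.

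**Conclusion.** The point holds as a gap in definitions. As written, a death outside hospital on treatment becomes a complete discontinuation with follow-up to 31 Dec 2019, except where supply plus 30 days passes that date. In-hospital deaths could be treated the same way under Protocol 9.1 and SAP 8.2. Compared with censoring at death, discontinuation and follow-up time are too high and 3- and 6-month persistence too low.

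The size cannot be derived from the documents. The illustrative range rests entirely on assumed mortality, place of death and discontinuation, and runs from trivial to material. The error may be larger in the active-cancer cohort, but need not be. No sample size or power figure is affected. This should be corrected, but it does not undermine the study.

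**What to change.** 1. Reconcile the Protocol abstract with Protocol 9.1 and SAP 8.2 so that in-hospital death ends Phase I follow-up and takes precedence over discontinuation. Label the row in Tables 5-8 as in-hospital death.
2. Keep the present discontinuation definition as the main analysis. In Tables 5-8, split discontinuers into those with and those without a claim of any type after end of supply plus 30 days. Label the second group as no further claims, possible death outside hospital. Censor administratively the patients whose supply plus 30 days passes 31 Dec 2019, and keep them out of that group.
3. Add a sensitivity analysis of the Kaplan-Meier discontinuation curves and of 3- and 6-month persistence, by treatment group and cancer cohort, that censors the no-further-claims patients at end of supply. Present the two definitions as a range.
4. In that sensitivity analysis, end follow-up for these patients at the later of last claim and end of supply, so that treatment time cannot outlast follow-up.
5. State the limitation in Protocol 9.9.

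The cost is wording plus programming on claims of all types for cohort members. The downside is that the no-further-claims group will include some living patients, especially late entrants, and some true stoppers who died later. That is why both definitions should be reported.
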